## 6.1 DETERMINATION OF SAMPLE SIZE

### 6.1.1 Dose Escalation

Approximately 24–30 patients will be enrolled in the dose-escalation stage. The exact number of patients to be enrolled in the study will depend upon the observed safety and pharmacokinetic/pharmacodynamic profile according to the dose-escalation rules (Section 3.1.1.2).

The operating characteristics of the dose-escalation stage of this study are shown in [Table 6](#), which provides the probability of escalation to the next higher dose for each underlying true DLT rate. For example, for a toxicity that occurs in 5% of patients, there is a >95% probability of escalating. Conversely, for a common toxicity that occurs with a rate of 70%, the probability of escalating is <5%.

**Table 6 Probability of Escalation to the Next Dose**

True underlying DLT rate	5%	10%	20%	30%	40%	50%	60%	70%	80%	90%
Probability of escalating the dose	97%	91%	71%	49%	31%	17%	8%	3%	1%	0.10%

DLT = dose-limiting toxicity.

[Table 7](#) shows the probability of failing to observe toxicity in a sample size of 3 patients given various true underlying toxicity rates. For example, with 3 patients, the probability of failing to observe toxicity occurring at least 60% of the time is less than 7%.

**Table 7 Probability of Failing to Observe Toxicity**

True underlying DLT rate	5%	10%	20%	30%	40%	50%	60%	70%	80%	90%
Probability of failing to observe toxicity (n=3)	86%	73%	51%	34%	22%	13%	6.40%	2.70%	0.80%	0.01%

DLT = dose-limiting toxicity.

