### **3.1.1.2 Starting Dose, Dose-Escalation Rules, and Determination of the Maximum Tolerated Dose**

The starting dose of DHES0815A is 0.6 mg/kg administered by IV infusion Q3W to patients in the first cohort. The dose may be increased by up to 100% of the preceding dose level for each successive cohort until a safety signal (defined as a DLT in 1 patient or study drug-related Grade  $\geq 2$  major organ adverse events (unless present at baseline) in at least 2 patients during the DLT assessment window in a given cohort) is observed. Once a safety signal has been observed in a given cohort, the dose may be increased by up to 50% of the preceding dose level for each successive cohort. Intrapatient dose escalation may be allowed for some patients (see Section 3.1.1.3).

Dose escalation of DHES0815A will occur in accordance with the rules listed below.

- A minimum of 3 patients will initially be enrolled in each cohort.
- If none of the first 3 DLT-evaluable patients experiences a DLT, enrollment of the next cohort at the next highest dose level may proceed.
- If 1 of the first 3 DLT-evaluable patients experiences a DLT, the cohort will be expanded to 6 patients. If there are no further DLTs in the first 6 DLT-evaluable patients, enrollment of the next cohort at the next highest dose level may proceed.
- If 2 or more DLT-evaluable patients in a cohort experience a DLT, the MTD will have been exceeded and dose escalation will stop. An additional 3 patients will be evaluated for DLTs at the preceding dose level, unless 6 patients have already been evaluated at that level. However, if the dose level at which the MTD is exceeded is  $\geq 15\%$  higher than the preceding dose level, 6 patients may be evaluated at an intermediate dose level.
- If the MTD is exceeded at any dose level, the highest dose at which fewer than 2 of 6 DLT-evaluable patients (i.e.,  $< 33\%$ ) experience a DLT will be declared the MTD.
- If the MTD is not exceeded at any dose level, the highest dose administered in this study will be declared the maximum administered dose (MAD).
- As long as the MTD has not been exceeded, additional patients may be enrolled at a given dose level in a given arm to explore factors influencing adverse events or to accumulate additional safety data.

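### Does the 0.01% in the 90% column of Table 7 misstate how well a 3-patient cohort detects toxicity in a way that matters?

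*Combined protocol and SAP*

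**What the plan says.** Section 6.1.1 supports the dose-escalation stage with two tables. Table 6 gives the probability of escalating at each true DLT rate. The text introducing Table 7 says that it "shows the probability of failing to observe toxicity in a sample size of 3 patients given various true underlying toxicity rates". The columns of Table 7 are headed "True underlying DLT rate" and run from 5% to 90%. The row is labelled "Probability of failing to observe toxicity (n=3"), and its last cell, under 90%, reads 0.01%.

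The text draws one reading from Table 7: with 3 patients, "the probability of failing to observe toxicity occurring at least 60% of the time is less than 7" per cent.

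The rule that Table 6 evaluates is in Section 3.1.1.2. Escalation may proceed on either of two paths. The first is "If none of the first 3 DLT-evaluable patients experiences a DLT". The second starts with one DLT among the first three, after which the cohort grows to six: "If there are no further DLTs in the first 6 DLT-evaluable patients", the next dose level may open.

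**The concern.** Tables 6 and 7 are the only operating characteristics given for the 3-patient cohorts, and this is a first-in-human study. A reader who cubes 0.1 gets a miss probability ten times the printed one. The error also runs in the flattering direction, because it makes a small cohort look better at detecting a very common toxicity than it is. Two tables in the same section then disagree at a 90% rate, since the chance of escalating cannot be smaller than the chance of seeing no DLT in three and should not be far above it here.

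If the cell reflected a wrong formula or a different sample size, the whole row would be in doubt, and with it the description of what a cohort of three can detect. That possibility is what makes the cell worth checking.

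**Working it through.** **Inputs.** The sample size is n = 3 (row label and introductory text of Table 7). The true rates p are the ten column headings. The escalation paths are those of Section 3.1.1.2. The printed values are those of Tables 6 and 7.

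**Step 1: reproduce Table 7.** The probability of no toxicity in three independent patients is (1 − p)³.

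| p | (1 − p)³ | Printed |
|---|---|---|
| 5% | 85.7% | 86% |
| 10% | 72.9% | 73% |
| 20% | 51.2% | 51% |
| 30% | 34.3% | 34% |
| 40% | 21.6% | 22% |
| 50% | 12.5% | 13% |
| 60% | 6.4% | 6.40% |
| 70% | 2.7% | 2.70% |
| 80% | 0.8% | 0.80% |
| 90% | 0.10% | 0.01% |

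Nine of ten cells agree, so the formula and n = 3 are what the authors used. Only the last cell differs: 0.10% − 0.01% = 0.09 percentage points.

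**Step 2: look for another reading of the cell.** With n = 4, 0.1⁴ = 0.01%, which matches. But n = 4 would make the first nine cells 81.5, 65.6, 41.0, 24.0, 13.0, 6.25, 2.56, 0.81 and 0.16%, and the printed row is not that. With n = 3, a miss probability of 0.01% needs p = 1 − 0.0001^(1/3) = 95.4%, which is not the column heading. Rounding cannot turn 0.10% into 0.01% at two decimals. A misplaced digit is the simplest explanation.

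**Step 3: compare with Table 6.** Write q = 1 − p. The probability of escalating is q³ + 3pq² × q³. At p = 90%:

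- no DLT in the first three: 0.1³ = 0.1000%
- one DLT in three, then none in the next three: 3 × 0.9 × 0.1² × 0.1³ = 0.0027%
- total: 0.1027%, printed in Table 6 as 0.10%

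If the first term were 0.01%, the total would be 0.0100% + 0.0027% = 0.0127%, which does not print as 0.10%. The same formula gives 97.3, 90.6, 70.9, 49.4, 30.9, 17.2, 8.2, 3.2 and 0.88% at rates from 5% to 80%. These match Table 6 throughout, so Table 6 is sound and the Table 7 cell is the one in error.

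**Step 4: trace what uses the cell.**

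- The escalation rule in Section 3.1.1.2 counts DLTs and refers to no tabulated probability.
- The worked sentence on Table 7 covers rates of at least 60%. The largest miss probability in that range is 0.4³ = 6.4%, below 7% whichever figure stands in the last cell.
- The two worked sentences before it (above 95% at a 5% rate, below 5% at a 70% rate) come from Table 6: 97.3% and 3.2%.
- The estimate of 24–30 patients depends on how many cohorts the escalation rules require, not on Table 7.

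**Step 5: size in use.** The probability of seeing at least one event at a 90% rate is 1 − 0.001 = 99.90%, against 1 − 0.0001 = 99.99% implied by the printed cell.

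**The case for a change.** The best case for acting is that the figure is demonstrably wrong, it contradicts a neighbouring table, it errs in the favourable direction, and putting it right would alter one cell with no new analysis. A low impact does not make a wrong number right.

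The facts in that argument all stand. The argument does not show that the trial would be run, analysed or interpreted differently. The tenfold ratio sounds serious only because both figures are close to zero. At a 90% rate the message is the same with either: a toxicity that common would almost certainly appear among three patients. The columns that inform judgement about a cohort of three are those at low and moderate rates, where 86% down to 13% of cohorts would show nothing, and those cells are correct. Anyone who needs the 90% value can obtain it from the row label in one step, and Table 6 points to the same answer.

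**Conclusion.** The 90% cell of Table 7 should read 0.10%, not 0.01%. The discrepancy is 0.09 percentage points in one of ten cells, and it is a clerical slip rather than a fault of method. No escalation decision, worked example, sample-size statement or conclusion relies on it, so no change to the plan is called for.

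This rests on two assumptions. The first is that patients' outcomes are independent with a common rate, which the other nine cells show the authors also assumed. The second is that the digit was read correctly from the PDF. If it was misread, there is no error at all, and the conclusion is the same.

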### 6.1.2 Dose Expansion

At the RP2D, up to approximately 25 patients will be enrolled to further assess the safety, tolerability, and preliminary evidence of anti-tumor activity of DHES0815A.

This study is intended to obtain preliminary safety, PK, pharmacodynamic, and activity information in the safety-evaluable population. The sample sizes do not reflect any explicit power and type I error considerations.

*Efficacy analyses will be performed on an ongoing basis in close collaboration with the study investigators for the expansion portion of the study to guide potential early stopping of enrollment in the event of lack of efficacy. Decisions to stop enrollment into the expansion cohort for futility will be made based on the totality of the available data, taking into account both safety and efficacy. Anti-tumor activity will be summarized by cohorts with an 80% CI. For example, in a cohort with 25 patients, if 10 of 25 patients have CR or PR, the objective response rate and its 80% CI will be summarized as 40% (27% –55%).*

*Continuous safety monitoring and interim analyses will be performed for the expansion portion of the study to guide potential early stopping of enrollment in the event of unacceptable toxicity. The first safety interim analysis will occur after approximately 6 patients complete 2 cycles in the expansion cohort or every 6 months, whichever occurs first.*

*A Bayesian posterior probability approach (Thall and Simon 1994) will be used to evaluate the toxicity in the expansion cohorts, including the rate of DLT-equivalent events that occur during Cycle 1 of study treatments. Events that are DLT-equivalent in the expansion cohort are defined by the same criteria used to identify DLT events in the dose-escalation cohorts (Section 3.1.1.1). During continuous safety monitoring or in an interim analysis, if the number of observed DLT-equivalent events indicates that there is an approximately 80% chance that the true DLT rate is  $\geq 25\%$ , accrual to the cohort may be paused. The Medical Monitor and Safety Scientist will determine whether further enrollment in the cohort should be halted and may provide other recommendations as described in Section 3.1.1. The final decision will be based on the totality of the observed DLT-equivalent events, other safety events, as well as feedback from study investigators, Biostatistics, and Clinical Pharmacology. Table 8 provides examples that cover scenarios with different true DLT-equivalent event rate assumptions. The examples show the number of observed DLT-equivalent events that might lead the Sponsor to stop enrollment and the corresponding operating characteristics using the posterior probability approach with a non-informative prior beta (1,1) and the stopping criteria stated above.*

**Table 8 Examples of Early Stopping Rules Based on DLT-Equivalent Event Rate in an Expansion Cohort**

Number of patients	Number of events to recommend stopping enrollment	Probability of early stopping for DLT		
		If true DLT rate = 40%	If true DLT rate = 30%	If true DLT rate = 20%
6	≥ 3	46%	26%	10%
12	≥ 5	56%	28%	7%
18	≥ 6	79%	47%	13%

DLT = dose-limiting toxicity (equivalent events).

Note: Recommend stopping enrollment if there is an approximately 80% chance that the true DLT rate is ≥ 25%.

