*During continuous safety monitoring or in an interim analysis, if the number of observed DLT-equivalent events indicates that there is an approximately 80% chance that the true DLT rate is  $\geq 25\%$ , accrual to the cohort may be paused. The Medical Monitor and Safety Scientist will determine whether further enrollment in the cohort should be halted and may provide other recommendations as described in the protocol. The final decision will be based on the totality of the observed DLT-equivalent events, other safety events, as well as feedback from study investigators, Biostatistics, and Clinical Pharmacology. The protocol provides examples that cover scenarios with different true DLT-equivalent event rate assumptions. The examples show the number of observed DLT-equivalent events that might lead the Sponsor to stop enrollment and the corresponding operating characteristics using the posterior probability approach with a non-informative prior beta (1,1) and the stopping criteria stated above.*

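### Table 8 prints single-look probabilities for a rule that is applied repeatedly, so its 12- and 18-patient figures understate how often the stopping recommendation would be met

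*Combined protocol and SAP*

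**What the plan says.** Section 6.1.2 states: "Continuous safety monitoring and interim analyses will be performed for the expansion portion of the study to guide potential early stopping of enrollment". It describes one interim in terms of patient numbers: "The first safety interim analysis will occur after approximately 6 patients complete 2 cycles in the expansion cohort or every 6 months", whichever is sooner. The numbers of patients at later looks are not given.

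The rule is triggered as follows: "During continuous safety monitoring or in an interim analysis, if the number of observed DLT-equivalent events indicates" roughly an 80% posterior chance that the true DLT rate is at least 25%, "accrual to the cohort may be paused". The Medical Monitor and Safety Scientist then consider whether to halt enrollment, and the final decision draws on all the data.

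The text presents Table 8 as giving example event counts with the "corresponding operating characteristics using the posterior probability approach with a non-informative prior beta (1,1) and the stopping criteria stated above". The synopsis (Determination of Sample Size) says the same: "The examples show the number of observed DLT-equivalent events that might lead the Sponsor to stop enrollment and the corresponding operating characteristics".

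Table 8 heads its three probability columns "Probability of early stopping for DLT". The rows are at least 3 events in 6 patients, at least 5 in 12 and at least 6 in 18. Neither the table, its note nor the text says whether the cells are per-look or cumulative.

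**The concern.** The operating characteristic of a repeatedly applied rule is the probability that it has triggered at or before a given point. That probability cannot decrease as patients accrue, yet the 20% column goes down from 10% to 7% before rising to 13%. The cells therefore cannot be cumulative, although the heading and the text invite that reading.

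Table 8 is the only place where the plan shows how often a cohort with a given true DLT rate would meet the recommendation. Someone reading 13% in the last row as the chance of wrongly flagging a cohort whose true rate is 20%, below the 25% limit, would be too optimistic. The table also stops at 18 patients, although about 25 may be enrolled.

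**Working it through.** **Inputs.** From Section 6.1.2: Beta(1,1) prior, toxicity limit 25%, posterior cut-off of about 80%. From Table 8: boundaries 3/6, 5/12 and 6/18; true rates 40%, 30% and 20%. Looks at exactly 6, 12 and 18 evaluable patients are an assumption, taken from the table's rows.

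**1. Boundaries.** After k events in n patients the posterior is Beta(1+k, 1+n−k). P(rate ≥ 0.25) is:

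| n | At the boundary | One event fewer |
|---|---|---|
| 6 | 3 events: 0.929 | 2 events: 0.756 |
| 12 | 5 events: 0.920 | 4 events: 0.794 |
| 18 | 6 events: 0.825 | 5 events: 0.668 |

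The boundaries agree with a single cut-off above 0.794 and at most about 0.825.

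**2. Reproducing Table 8.** The single-look tail P(X ≥ r), with X ~ Binomial(n, p), gives:

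| n (r) | p = 40% | p = 30% | p = 20% | Printed |
|---|---|---|---|---|
| 6 (3) | 45.57% | 25.57% | 9.89% | 46/26/10 |
| 12 (5) | 56.18% | 27.63% | 7.26% | 56/28/7 |
| 18 (6) | 79.12% | 46.56% | 13.29% | 79/47/13 |

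All nine cells match after rounding.

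**3. Cumulative probability.** Carry the event count forward patient by patient and, at each look, remove the paths that have reached the boundary. For example, take p = 20% and the look at 12. Paths still running after 6 patients have 2, 1 or 0 events, with probabilities 0.2458, 0.3932 and 0.2621. To reach 5 they need at least 3, 4 or 5 events in the next 6 patients, with probabilities 0.0989, 0.0170 and 0.0016. New triggers are 0.2458×0.0989 + 0.3932×0.0170 + 0.2621×0.0016 ≈ 0.0314. The cumulative value is 9.89% + 3.14% = 13.03%. The same recursion throughout gives:

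| By n | p = 40% | p = 30% | p = 20% |
|---|---|---|---|
| 6 | 45.57% | 25.57% | 9.89% |
| 12 | 63.28% | 36.12% | 13.03% |
| 18 | 82.24% | 52.70% | 19.00% |

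Simulation agrees to within about 0.2 percentage points.

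**4. Gap.** Cumulative minus single-look is 7.1/8.5/5.8 points at n=12 and 3.1/6.1/5.7 points at n=18. At p = 20% the ratios are 13.03/7.26 = 1.8 and 19.00/13.29 = 1.4. At a true rate of exactly 25%, single-look values are 16.9/15.8/28.3% and cumulative values 16.9/23.4/34.9% at 6/12/18.

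**5. More frequent looks (illustration only).** Suppose the rule is checked after every patient, with each Cycle 1 outcome known before the next check. At p = 20%, the chance of triggering by 18 patients is 27.6–28.5% if checks start at the 6th patient, over the cut-offs compatible with Table 8. With a cut-off of 0.80 it is 36.7% if they start at the 3rd patient and 49.6% if they start at the 1st. The starting point matters far more than the exact cut-off.

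**The case against.** The strongest reply is that nothing in Table 8 is miscalculated. The table is titled as examples, each row is complete in itself, and a statistician can see from the 20% column that the cells are per-row. No row claims to be cumulative. Looks at 12 and 18 are not planned anywhere, so the replacement figures rest on an assumed schedule, and a calendar-driven look could fall at another sample size. The rule is advisory, Section 6.1.2 disclaims power and type I error considerations for the sample size, and Section 3.1.2 separately allows accrual to be halted for toxicity.

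Much of this stands, and it limits the weight of the point. The figures 63/36/13% and 82/53/19%, and the ratios 1.8 and 1.4, are conditional on looks at 6, 12 and 18. They describe meeting a recommendation, not an actual halt. The per-patient figures are too sensitive to the starting point to serve as more than an illustration.

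The reply does not remove the defect. The plan offers these cells as the operating characteristics of a rule it says will be applied during continuous monitoring, and single-look tails are not that. Being an example does not excuse an unclear label, and disclaiming error control does not make a printed probability right. The missing schedule is part of the problem.

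**Conclusion.** The concern holds. Table 8's arithmetic and boundaries are correct, and its 6-patient row is right as a first look. Read as properties of the repeated rule, the 12- and 18-patient rows are too low. With looks at 6, 12 and 18 and every patient's Cycle 1 outcome known at each look, the understatement is about 3 to 8 percentage points. At a 20% true rate the chance of a false trigger by 18 patients is 19%, where the table prints 13%. These figures do not depend on the exact cut-off, given Table 8's boundaries, and they are a floor for any schedule that includes those three looks.

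The consequence is modest. A high true rate is flagged more often than printed, so patient protection is not weakened. What is understated is how often an acceptable cohort would be put up for a pause. This should be corrected, but it does not undermine the design.

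**What to change.** - Relabel Table 8's existing probability columns as per-look probabilities.
- State in Section 6.1.2 the number of evaluable patients at which the rule is first applied and when later looks occur.
- Add cumulative triggering probabilities for that schedule, up to about 25 patients. If the looks are 6/12/18, the values at 40/30/20% are 46/26/10%, 63/36/13% and 82/53/19%.
- State the exact posterior cut-off. The note says only "Recommend stopping enrollment if there is an approximately 80% chance that the true DLT rate is" at least 25%, and 4 events in 12 give 0.794, which could be read as meeting it although the table requires 5. The choice also affects later boundaries: at 25 patients a cut-off of 0.80 gives 8 events and 0.825 gives 9. A final look at 25 added to 6/12/18 would then give 89.3/60.5/21.5% or 85.4/55.2/19.5% respectively.

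The cost is relabelled columns, added columns and two sentences, with the matching synopsis text. The boundaries at 6, 12 and 18 stay as they are, and no patients or procedures are added. The only downside is a less favourable stated chance of a false trigger.

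### Table 8 is correct for a single look at a hard 80% cut-off, but the text describes a looser, continuously applied rule whose stopping probabilities the table does not show

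*Combined protocol and SAP*

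**What the plan says.** The threshold appears three times. The synopsis (Determination of Sample Size) and Section 6.1.2 both act when the event count "indicates that there is an approximately 80% chance that the true DLT rate is" at least 25%. The note under Table 8 repeats it: "Recommend stopping enrollment if there is an approximately 80% chance that the true DLT rate is" at least 25%. None of the three gives a tolerance for the word approximately.

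Section 6.1.2 says when the rule operates: "During continuous safety monitoring or in an interim analysis, if the number of observed DLT-equivalent events indicates" the stated chance, accrual to the cohort may be paused. Continuous monitoring and interim analyses are named separately, and no minimum number of patients is given for the former. For the latter, "The first safety interim analysis will occur after approximately 6 patients complete 2 cycles in the expansion cohort or every 6 months", whichever comes first.

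Section 6.1.2 presents Table 8 as examples of event counts with their operating characteristics, obtained "using the posterior probability approach with a non-informative prior beta (1,1) and the stopping criteria stated above". The table recommends stopping at 3 or more events in 6 patients, 5 or more in 12, and 6 or more in 18. It heads the remaining columns as probabilities of early stopping at true rates of 40%, 30% and 20%.

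**The concern.** A reader will take Table 8 as the behaviour of the rule in the text. The two differ in three respects:

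- **Cut-off.** The text's threshold is approximate; the table's is exact. They disagree on 4 events in 12 patients.
- **Start.** The uniform prior alone puts 75% of its mass at or above 25%, so very little data is needed to pass 80%. With no minimum number of patients, a lone early event satisfies the rule.
- **Repetition.** A rule checked repeatedly is crossed more often than one checked once, and the tabled figures are single-look.

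At stake is how often the sponsor, investigators and ethics committees should expect the monitoring rule to fire. That matters most at a true rate of 20%, which is below the 25% reference and where a trigger is a false alarm.

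**Working it through.** **Inputs.** Prior Beta(1,1), reference rate 25%, threshold about 80% (Section 6.1.2 and Table 8 note); looks at 6, 12 and 18 (Table 8); cohort up to about 25 (Section 6.1.2).

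**Step 1: boundaries.** With x events in n patients the posterior is Beta(1+x, 1+n−x), and P(rate ≥ 25%) equals P(Bin(n+1, 0.25) ≤ x).

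| n | one event below the boundary | at the boundary |
|---|---|---|
| 6 | 2 events: 75.6% | 3 events: 92.9% |
| 12 | 4 events: 79.4% | 5 events: 92.0% |
| 18 | 5 events: 66.8% | 6 events: 82.5% |

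Thus 3, 5 and 6 are the smallest counts that reach at least 80%.

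**Step 2: tabled probabilities.** These are binomial tails P(X ≥ boundary) at one look, for true rates of 40/30/20%:

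- n=6: 45.6/25.6/9.9% (table 46/26/10)
- n=12: 56.2/27.6/7.3% (table 56/28/7)
- n=18: 79.1/46.6/13.3% (table 79/47/13)

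All nine reproduce.

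**Step 3: the word approximately.** At n=6 and n=18 the nearest lower counts (75.6% and 66.8%) are well short of 80%. Only n=12 depends on the reading, because 79.4% rounds to 79% and is approximately 80% in ordinary usage. If 4 of 12 counted, cumulative triggering by n=18 with looks at 6, 12 and 18 would be 85.9/59.8/25.3% instead of 82.2/52.7/19.0%, a difference of 3.6 to 7.1 percentage points. With a look after every patient from the sixth it would be 87.9/64.0/29.8% instead of 87.2/62.6/28.5%, a difference of under 1.5 points, because 4 events already trigger at n = 9 to 11.

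**Step 4: the first patients.**

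- 1 of 1: posterior Beta(2,1), so 1 − 0.25² = 93.8%.
- 1 of 2: posterior Beta(2,2), so 1 − (3×0.25² − 2×0.25³) = 84.4%.
- 1 of 3: 73.8%, no trigger.

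The chance of at least one event in the first two patients is 1 − (1−p)²: 19% at a true 10%, 36% at 20%.

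**Step 5: repeated looks.** At each n I took the smallest count with a posterior of at least 80%: 1 for n=1–2, 2 for n=3–5, 3 for n=6–8, 4 for n=9–11, 5 for n=12–15, 6 for n=16–18, 7 for n=19–22, 8 for n=23–25. The distribution of event counts that had not yet crossed was carried forward patient by patient, adding up the probability that crossed.

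| Triggered by n=18 | 40% | 30% | 20% |
|---|---|---|---|
| Table 8, last row | 79% | 47% | 13% |
| Looks at 6, 12, 18 | 82% | 53% | 19% |
| Every patient from n=6 | 87% | 63% | 28% |
| Every patient from n=1 | 92% | 76% | 50% |

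**Step 6: effect of a start at n=6, by n=25.**

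| True rate | from n=1 | from n=6 |
|---|---|---|
| 10% | 22% | 5% |
| 20% | 51% | 31% |
| 30% | 79% | 69% |
| 40% | 95% | 92% |

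**The case against.** The strongest reply is that nothing in Table 8 is wrong. Its boundaries and probabilities follow exactly from the stated prior and an 80% cut-off, and its n=12 row shows which reading of the threshold was intended. It is titled and introduced as examples, so starting at n=6 does not contradict a rule that also operates earlier, and n=6 fits the first planned interim. A trigger does not bind: accrual may be paused, the Medical Monitor and Safety Scientist then decide, and the final decision uses all the data. Section 3.1.2 separately halts accrual if toxicity suggests that the MTD has been exceeded.

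All of that stands. It rules out two stronger readings that a reader might infer. One is that Table 8 contains an arithmetic error; Steps 1 and 2 show that it does not. The other is that the n=12 row ought to be 4; the documents do not require this, since 5 is the correct boundary for a hard 80% cut-off. Nor does 4 of 12 oblige enrolment to continue.

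The reply does not supply a minimum number of patients for continuous monitoring. Nor does it make single-look probabilities describe repeated looks, although Section 6.1.2 offers them as the operating characteristics of the stated criteria.

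**Conclusion.** The point holds as a mismatch between text and table, not as a calculation error. The text leaves the cut-off loose and the starting point open, and the tabled probabilities are those of one isolated look. At a true rate of 20%, the last row shows 13% while the chance of at least one trigger by 18 patients is 19%, 28% or 50%, depending on which monitoring schedule is meant.

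These figures assume independent patients with a common event rate, Cycle 1 outcomes known in enrolment order at each look, and a hard 80% cut-off. They count first crossings of the criterion, not actual halts of enrolment; because a trigger is advisory, the actual halting rate could be lower. For the same reason the severity is modest, but the ambiguity concerns when the expansion-stage safety review is set off, and it is cheap to remove.

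**What to change.** 1. Keep the boundaries 3, 5 and 6, and replace approximately 80% with at least 80% in the synopsis, Section 6.1.2 and the note to Table 8.
2. State the smallest number of patients at which the posterior rule is applied. Six would match the table's first row and the first planned interim, with individual DLT-equivalent events still reviewed as they are reported.
3. Label the Table 8 probabilities as single-look, or replace them with cumulative values for the monitoring schedule to be used.

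The cost is wording in three places and a table label or recalculation; no change to sample size or data collection. The statistical cost of starting at six patients should be disclosed. By n=25 it lowers triggering from 22% to 5% at a true rate of 10% and from 51% to 31% at 20%, but it also lowers detection from 79% to 69% at 30% and from 95% to 92% at 40%. It also leaves the first five patients without a formal posterior trigger: 2 events in 3 patients, for example, give 94.9% and would rest on medical review alone.
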